## 2.2 ENDPOINTS

### Co-Primary Endpoints

- To assess whether the median progression-free survival is longer in third-line patients with chemo-refractory metastatic colorectal cancer receiving Axitinib monotherapy Versus placebo
- To assess whether the median progression-free survival is shorter in those patients who do not undergo vascular shutdown (defined as  $\leq 20\%$  reduction in CEHPI at 2 weeks) compared with those that do undergo vascular shutdown ( $>20\%$  reduction in CEHPI at 2 weeks).

### Secondary Endpoints

- To compare overall survival between the treatment and placebo arms
- To compare duration on study treatment between the treatment and placebo arms
- To compare the best overall RECIST response rate between the treatment and placebo arms
- To compare and correlate the 2-week CEHPI perfusion index and 8 week RECIST response rates in the ITT population
- To compare the median overall survival of patients receiving Axitinib who develop new diastolic hypertension ( $>90\text{mmHg}$ ) with those that do not (in either/or the blinded placebo group or treatment group combined)
- To identify if CEHPI will function as a correlative biomarker of Axitinib pharmacokinetics (PK) and help minimise toxicity and identify responders
- To compare toxicity (CTC) information for the treatment and placebo arms.
  - Type, incidence, severity, timing, seriousness of adverse events by Chemotherapy toxicity criteria (CTC) v4.03 grading.
- Axitinib PK analysis correlation with patients developing or not developing diastolic hypertension

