### 1.3. Axitinib Molecular Formula and Molecular Activity

[figure not shown]
Axitinib, a substituted indazole derivative, is an oral, potent, and selective inhibitor of vascular endothelial growth factor (VEGF) receptors 1, 2, and 3.

**Figure 2: The molecular formula of Axitinib is  $C_{22}H_{18}N_4OS$ . It has a molecular weight of 386.47. The chemical name is N-Methyl-2-[3-((E)-2-pyridin-2-yl-vinyl)-1H-indazol-6-ylsulfanyl]-benzamide.**

Phase 2 studies with axitinib are ongoing or completed in various tumour types, including metastatic breast cancer (Protocol A4061010), non-small cell lung cancer (Protocol A4061011), cytokine-refractory renal cell carcinoma (RCC; Protocol A4061012, A4061035), radioiodine [ $^{131}I$ ]-refractory thyroid cancer (Protocol A4061014), malignant melanoma (Protocol A4061015), advanced pancreatic cancer (Protocol A4061016), colorectal cancer (CRC; Protocol A4061020, A4061034), sorafenib-refractory RCC (Protocol A4061023), iodine and doxorubicin-refractory thyroid cancer (Protocol A4061027), and non-small cell lung cancer (NSCLC; Protocol A4061030, A4061038, A4061039). A pivotal Phase 3 study in advanced pancreatic cancer (Protocol A4061028) was terminated early for futility.

Retrospective analyses of five AG-013736 Phase 2 studies across multiple tumour types (RCC, melanoma, NSCLC, and thyroid cancer) demonstrated that patients who developed at least one in-clinic measurement of dBP >90 mmHg at any point during treatment had significantly better clinical outcomes for OS (30.1 vs 10.2 months; hazard ratio [HR]=0.546;  $p<0.001$ ), PFS (13.1 vs 5.8 months; HR=0.42;  $p<0.001$ ), and ORR (43.9% vs 12.0 %;  $p<0.001$ ). Figure 2: below shows the association between transient dBP > 90 mmHg with longer median OS.

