### 3. Study Design

A Phase II, double-blind, 2 arm pilot randomised placebo controlled trial. 50 patients will be sequentially randomised 2:1 to Axitinib or placebo.

Inclusion criteria: Chemorefractory third-line metastatic CRC with US-assessable liver or other abdominal metastases that can have a baseline DCEUS baseline measurement.

Treatment arm: Axitinib monotherapy started in all patients at 5mg bd, and increased fortnightly by a dose level (See Table 4) as tolerated to a maximum dose of 10mg bd.

Control arm: Placebo (blinded) randomised 2:1 to Axitinib : placebo

Follow up: Outpatient monitoring at 2 weeks and 4 weeks post first dose then 4 weekly thereafter with RECIST restaging every 8 weeks. CEHPI at baseline, 2 weeks and 8 weeks for assessment of differential blood supply (CEHPI) with an optional visit at 48-72 hours post first dose. VEGF-PK samples at Day 15 & Day 28 and at 8 weeks and RECIST progression. At 8 weeks, after tumour CT RECIST assessments, conventional responders (CR/PR/SD) continue monotherapy. In non-responders (PD), monotherapy can be continued if patient chooses to continue and if tolerated. CT response assessments continue at 8 weekly intervals in all patients, with parallel 8 weekly DCE-US. CEHPI at baseline, optionally at 47-72 hours, 2 weeks, 8 weeks and at progression of disease.

[figure not shown]

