The conventional PFS and OS for this cohort of chemo-refractory patients is 6-8 weeks and 4-6 months respectively. This is the first study with Axitinib in this setting. Our aim with 50 patients is to generate data for a sample size calculation for a randomised phase III. In the only comparative Phase 2 study (A6181003) with a similar compound, is of Sunitinib in chemorefractory metastatic colorectal cancer, 84 patients were enrolled and 82 were actually treated with Sunitinib. 10% discontinued due to adverse events. The ITT analyses for PFS was less than 2 months but OS still showed an encouraging overall survival of 10.2 months. Of greater interest, 1 patient with prior Bevacizumab therapy had a partial response; 24 patients (29%) had a best response of stable disease, 13 patients had SD  $\geq 22$  weeks. (This demonstrates the reason for doing our analysis as a sub-population has benefited significantly from Axitinib's parent compound and with CEPHI – we hope to predict this group). In our study, we would thus expect around 15-18 of the treated patients to have prolonged progression-free survival of this order of magnitude, and the placebo treated patients will act as a contemporaneous control. If the 2 week CEPHI index is highly predictive of survival in this group, then selection on this basis for a phase III trial will enrich the potentially benefitting population even further.

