## 9.2 Statistical analysis plan

The primary analysis will be on PFS by Kaplan-Meier of patients who manage to complete at least 2 weeks of Axitinib therapy (versus Placebo).

For the secondary analyses:-

A stratified log-rank test (1-sided,  $p=0.025$ ) will be used to compare PFS between CEHPI responders and non-responders. The median event time and 2-sided 95% CI for the median will be provided. The hazard ratio and its 95% CI will be also estimated.

The optimum CEHPI cut-point for determining response will be confirmed using the percentage change in CEHPI against RECIST response using a receiver operator characteristic curve. Test statistics including sensitivity, specificity, positive predictive value, negative predictive value, odds of disease progression and area under the curve will be calculated for 2 week CEHPI reduction in predicting disease progression.

A similar analysis will be performed with diastolic blood pressure.

Overall survival is defined as the time from date of randomisation to date of death due to any cause. For patients not expiring, their survival times will be censored at the last date they are known to be alive. Patients lacking data beyond the day of randomisation will have their survival times censored at the date of randomisation with duration of 1 day. Overall survival will be summarised using Kaplan-Meier methods and displayed graphically where appropriate. A stratified log-rank test (1-sided,  $p=0.025$ ) will be used to compare OS between CEHPI responders and non-responders. The median event time and 2-sided 95% CI for the median will be provided. The hazard ratio and its 95% CI will be also estimated.

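### The overall survival comparison by new diastolic hypertension sets no classification window, so counting survival from randomisation builds in immortal-time bias towards the hypertensive group

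*Combined protocol and SAP*

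**What the plan says.** The same comparison appears in the Trial Summary, in section 2.1 and in section 2.2 (Secondary Endpoints): "To compare the median overall survival of patients receiving Axitinib who develop new diastolic hypertension" (above 90 mmHg) with those who do not. The population is left open by the phrase "in either/or the blinded placebo group or treatment group combined".

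Section 9.2 fixes the time origin: "Overall survival is defined as the time from date of randomisation to date of death due to any cause". Its only analysis text for blood pressure is "A similar analysis will be performed with diastolic blood pressure". That sentence follows the ROC paragraph and comes before overall survival is defined. A one-sided 0.025 stratified log-rank test "will be used to compare OS between CEHPI responders and non-responders". No test is named for the dBP groups.

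The hypothesis comes from the retrospective analyses in section 1.3, which classed as hypertensive "patients who developed at least one in-clinic measurement of dBP >90 mmHg at any point during treatment" and reported OS of 30.1 against 10.2 months (HR 0.546).

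For this comparison the plan gives no landmark, no time-dependent covariate and no restriction to patients alive at a fixed time. The 2-week time point belongs to CEHPI, and the rule of at least 2 weeks of therapy belongs to the primary PFS analysis.

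**The concern.** The grouping depends on what happens after randomisation, yet survival is counted from randomisation. To enter the hypertensive group a patient must live, and remain under blood pressure observation, until a reading above 90 mmHg is recorded. The time up to that reading cannot contain a death in that group. A patient who dies early has had few chances to qualify and is counted as non-hypertensive.

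Two features of the design lengthen the period in which a patient can qualify: fortnightly dose escalation and the option to continue treatment past progression. Against an expected median OS of only 4 to 6 months, a few weeks of guaranteed survival matter.

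If the arms are pooled there is a second problem. Hypertension is more likely on Axitinib, so placebo patients would collect in the non-hypertensive group, and any drug effect on survival would be credited to blood pressure.

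At stake is a misleading signal about blood pressure as a marker of benefit, in a study whose section 9.1 gives better selection of patients as its major exploratory interest.

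**Working it through.** The plan states no expected difference, event count or power for this comparison, so there is no figure to reproduce. The check asks what the comparison shows when dBP and death are unrelated.

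**Inputs from the documents**
- Survival: "The conventional PFS and OS for this cohort of chemo-refractory patients is 6-8 weeks and 4-6 months respectively". In weeks, OS is 4 × 52/12 = 17.3 to 6 × 52/12 = 26.
- Visits: "Outpatient monitoring at 2 weeks and 4 weeks post first dose then 4 weekly thereafter", that is weeks 2, 4, 8, 12 and so on, with clinic BP at each visit (section 7.3).
- Patients: 50 randomised 2:1, so about 33 on Axitinib.
- Share who can become hypertensive: 56/128 = 44% (single-agent solid tumour column, section 1.4), used as a proxy for new dBP above 90.

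**Assumptions**
- Exponential survival, with onset independent of death.
- Median onset of 1, 4, 8 or 12 weeks among susceptible patients.
- Detection either until progression (median 7 weeks) or until death.
- Censoring uniform over 52 to 104 weeks.
- One-sided 0.025 unstratified log-rank test, carried over from the CEHPI groups.

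**Step 1: the mechanism.** With exponential survival of median m, a patient first detected at week v has median OS of v + m. For m = 17.3, detection at week 4 gives 21.3 weeks and at week 8 gives 25.3. For m = 26, the values are 30 and 34. Blood pressure has done nothing to produce these gains.

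**Step 2: simulated size, 44% susceptible, readings at scheduled visits only.** Hazard ratios (ratio of death rates per person-time) and medians come from 400,000 patients, and false-positive rates from 3,000 trials of 33.

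| Median OS (weeks) | Detection until | Median onset (weeks) | Median OS, hypertensive vs not (weeks) | Gap (weeks) | HR | False-positive rate |
|---|---|---|---|---|---|---|
| 17.3 | progression | 1 | 19.8 vs 16.1 | 3.7 | 0.86 | 0.052 |
| 17.3 | progression | 4 | 21.9 vs 16.0 | 5.9 | 0.80 | 0.046 |
| 17.3 | progression | 8 | 23.5 vs 16.2 | 7.3 | 0.77 | 0.040 |
| 17.3 | death | 1 | 20.0 vs 15.3 | 4.7 | 0.83 | 0.075 |
| 17.3 | death | 4 | 23.9 vs 13.5 | 10.4 | 0.68 | 0.157 |
| 17.3 | death | 8 | 27.7 vs 13.3 | 14.4 | 0.60 | 0.238 |
| 26 | progression | 1 | 28.4 vs 24.7 | 3.7 | 0.90 | 0.035 |
| 26 | progression | 4 | 30.8 vs 24.6 | 6.2 | 0.84 | 0.041 |
| 26 | progression | 8 | 32.1 vs 24.7 | 7.4 | 0.81 | 0.028 |
| 26 | death | 1 | 28.7 vs 24.1 | 4.6 | 0.87 | 0.052 |
| 26 | death | 4 | 33.0 vs 21.5 | 11.6 | 0.73 | 0.109 |
| 26 | death | 8 | 37.3 vs 20.2 | 17.1 | 0.64 | 0.182 |

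The gap exceeds 6 weeks in 7 of these 12 rows.

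**Step 3: extremes.** With 12-week onset and detection until death, HR is 0.56 to 0.58 and the gap 16.4 to 20.5 weeks. With 80% susceptible (an upper assumption), HR falls as low as 0.40 and the gap reaches 27.9 weeks. At the other end, section 5.11 asks for home readings twice daily. If those count, early onset (median 1 to 2 weeks) gives HR 0.87 to 0.96 and a gap of about 1.5 to 4 weeks, and 4-week onset gives 0.82 to 0.89 and 4.6 to 6.0 weeks.

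**Step 4: landmark.** In the same visit-based scenarios, classifying by week 4 and counting OS from week 4 gives HR 0.99 to 1.01 and medians within about 0.3 weeks. The false-positive rate is 0.008 to 0.026 with 44% susceptible, and at most 0.048 with 80%, where groups are unbalanced. A week-8 landmark, checked with a 12% or 20% chance of first detection per visit, gave medians within 0.4 weeks and error of 1.5 to 2.9%.

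**Step 5: patients kept for OS**, 33 × 2^(−t/m):
- Week 4: 33 × 2^(−4/17.3) = 28.1 to 33 × 2^(−4/26) = 29.7.
- Week 8: 33 × 2^(−8/17.3) = 23.9 to 33 × 2^(−8/26) = 26.7.

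**Step 6: patients still progression-free**, with median PFS of 6 to 8 weeks:
- Week 2: 33 × 2^(−2/6) = 26.2 to 33 × 2^(−2/8) = 27.7.
- Week 4: 33 × 2^(−4/6) = 20.8 to 33 × 2^(−4/8) = 23.3.
- Week 8: 33 × 2^(−8/6) = 13.1 to 33 × 2^(−8/8) = 16.5.

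**The case against.** The endpoint does not literally say that patients are grouped over all follow-up. The sentence on a similar analysis follows the ROC text on 2-week CEHPI, so a fixed early dBP time point could be meant there. That ambiguity is real for the ROC. It does not rescue the OS comparison: the plan fixes a time for CEHPI and none for dBP, and its model analysis used any point during treatment.

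The size rests on inputs that the documents do not give. With early onset and frequent home readings the bias is modest. This stands, and it is why only a range is reported.

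The comparison is also one secondary item in a pilot that disclaims adequate power. Neither go-forward signal in section 9.1 (PFS by arm, survival by CEHPI group) uses blood pressure, and no part of the plan selects patients by it. This stands too and limits the severity.

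A reader might infer that the endpoint will come out positive by itself. The figures do not support that if positive means statistically significant: in the tabulated scenarios 76% to 97% of null trials would not be significant, and the endpoint names no test.

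**Conclusion.** The point holds as a should-fix matter. If groups are formed over all follow-up and OS runs from randomisation, the comparison is biased towards the hypertensive group, and this was so in every null scenario examined. The size is uncertain. With 44% susceptible, onset medians up to 8 weeks and either visit or home readings, the null hazard ratio is roughly 0.6 to 0.95 and the false gap in median OS about 2 to 17 weeks. The false-positive rate may exceed 0.025, provided the CEHPI log-rank test carries over.

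A reader might also infer that the artefact always exceeds the plan's 6-week meaningful difference. It does so in many scenarios but not all, and section 9.1 sets that threshold for PFS by arm and for CEHPI groups, not for dBP. The randomised PFS comparison is not affected.

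**What to change.** Before unblinding, amend sections 2.2 and 9.2 as follows.
- **OS by dBP, Axitinib arm:** classify patients by dBP above 90 mmHg up to a prespecified early scheduled visit, and compare OS from that visit among patients alive then. State whether clinic readings, home readings or both count.
- **Choice of visit:** week 4 keeps about 28 to 30 of 33 patients, and week 8 about 24 to 27. Week 8 captures more of the later-onset hypertension but loses 6 to 9 patients.
- **Supporting analysis:** a Cox model with hypertension as a time-dependent covariate. It drops no patients, but gives a hazard ratio and not a difference in medians.
- **Any PFS or ROC analysis of dBP:** use week 2 or week 4. Week 8 would leave about 13 to 17 of 33 patients progression-free and would coincide with the RECIST result that dBP is meant to predict.
- **Population:** name the arms included. If they are combined, stratify by arm.

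The cost is wording only, since the readings are already collected. Patients who die before the landmark leave that analysis, and hypertension that starts after it counts as absent there.

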## Study Design

A Phase II, double-blind, 2 arm pilot randomised placebo controlled trial. 50 patients will be randomised 2:1 to Axitinib or placebo.

Main Inclusion criteria: Chemo-refractory third-line metastatic CRC with US-assessable liver or other abdominal metastases that can have a baseline DCEUS baseline measurement.

Arm A: Axitinib monotherapy started in all patients at 5mg bd, and increased fortnightly by a dose level (See Table 4) as tolerated to a maximum dose of 10mg bd.

Arm B: Placebo at 2:1 ratio to treatment

Follow up: *Optional* visit at 48-72 hours post first dose for measurement of temperature, oxygen saturations, blood pressure and CEHPI. Outpatient monitoring at 2 weeks and 4 weeks post first dose and at 4 week intervals thereafter which will include medical history and examination, measurement of temperature, oxygen saturations and blood pressure, urinalysis and blood tests including GI profile and VEGF-PK samples. RECIST restaging at 8 weeks and at 8 weekly intervals thereafter. CEHPI will be performed at baseline, optionally at 48-72 hours, 2 weeks and 8 weeks for assessment of differential blood supply. At 8 weeks, after tumour CT RECIST assessments, conventional responders (CR/PR/SD) continue monotherapy. In non-responders (PD), monotherapy can be continued if patient chooses to continue and if tolerated.

[figure not shown]

Figure 1: Protocol for responders and non-responders to Axitinib at 8 week RECIST evaluation.

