#### **Secondary objectives of trial**

- To assess the correlation in patients with a confirmed vascular response (as evaluated by a greater than 20% reduction in CEPHI at 2 weeks).
  - This assessment will be done by separating out the RECIST-progressors (non-responders) who can also be detected by CEPHI at 2 weeks, and comparing this with RECIST responders (CR+PR+SD). The patients receiving Placebo will be included in this analysis.
  - To demonstrate the value of CEPHI as an early imaging selection biomarker of non-response (or response) in patients who have had at least 4 weeks of study treatment.
- To compare overall survival between the treatment and placebo arms
- To compare the overall RECIST response rate between the treatment and placebo arms
- To compare and correlate the 2 week CEPHI and 8 week RECIST response rates.
- To compare the median overall survival of patients receiving Axitinib who develop new diastolic hypertension (>90mmHg) with those that do not (in either/or the blinded placebo group or treatment group combined)
- To identify if CEPHI will function as a non-invasive correlative biomarker of Axitinib pharmacokinetics (PK) and help minimise toxicity and identify responders

CONFIDENTIAL

- Toxicity (CTC) i for the treatment and placebo arms

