### **6.6 Survival Follow-up**

All patients will be followed for survival every 2 months for at least 1 year after randomisation of last patient. Information regarding systemic therapy, radiation or local therapy, and surgery during survival follow up will also be collected. Premature termination of this clinical trial may occur because of a Imperial College decision, regulatory authority decision, change in opinion of the IRB/IEC, drug safety problems, or at the discretion of Pfizer. In addition, Pfizer retains the right to discontinue development of Axitinib at any time.

Regardless of the reason for termination, all data available for the patient at the time of

discontinuation of follow-up must be recorded in the CRF. All reasons for discontinuation of treatment must be documented. In terminating the study, the investigators will ensure that adequate consideration is given to the protection of the patients' interest.

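### The diastolic-hypertension survival endpoint leaves its comparison group open and lets placebo patients in without adjustment for arm, so part or all of a drug effect on survival could be read as a hypertension effect

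*Combined protocol and SAP*

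**What the plan says.** Section 2.2 (Secondary Endpoints) sets out "To compare the median overall survival of patients receiving Axitinib who develop new diastolic hypertension", defined as above 90 mmHg, against patients who do not. It then qualifies the comparison group as "in either/or the blinded placebo group or treatment group combined". The same qualification appears in the secondary objectives of the Trial Summary and of section 2.1.

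The only analysis text is one sentence in section 9.2: "A similar analysis will be performed with diastolic blood pressure". It directly follows the paragraph on the ROC curve for the perfusion index (CEHPI). It names no comparator, no adjustment for arm, no time at which pressure status is fixed and no test. The one-sided 0.025 log-rank test in that section is stated for CEHPI responders against non-responders only.

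Section 1.3 gives the origin of the hypothesis: retrospective analyses of Phase 2 studies of the drug, grouping patients by whether they ever had a raised diastolic reading during treatment. The plan does not say that it adopts that grouping as its comparator.

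**The concern.** The index group is described as Axitinib patients. The comparison group may be wholly on Axitinib, wholly on placebo, or a mixture. When it includes placebo patients, hypertension status and treatment are entangled: everyone with the marker is on drug, and some or all of those without it are not. If Axitinib prolongs survival and hypertension says nothing about who benefits, the contrast will still favour the hypertensive group.

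Because the wording allows several contrasts, the choice can also be made after the data are seen. The pilot is meant to inform the selection of patients for a later trial, so a marker signal that is only the treatment effect would be a poor guide.

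**Working it through.** **Readings that the wording allows**
- (a) Axitinib hypertensives v Axitinib non-hypertensives
- (b) Axitinib hypertensives v placebo non-hypertensives
- (c) Axitinib hypertensives v non-hypertensives of both arms
- (d) hypertensives v non-hypertensives, both pooled over arms

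The plan gives no event count or power for this endpoint, so there is no figure to reproduce. The check is what each reading reports when hypertension is uninformative.

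**Inputs**
- Size: "50 patients will be randomised 2:1 to Axitinib or placebo" (Study Design). 50 × 2/3 = 33.3 and 50 × 1/3 = 16.7, so 33 and 17.
- Control median OS: 5 months (21.7 weeks), the middle of the 4-6 months in section 9.1.
- Hypertension on Axitinib: 56/128 = 44% (Table 1, single-agent solid-tumour column). This is an adverse-event rate used as a proxy for diastolic pressure above 90. 33 × 0.44 = 14.5, about 15 patients.
- Hypertension on placebo: 10-20%, assumed.
- Drug OS hazard ratio (HR): assumed; 1.0, 0.7 and 0.6 shown.
- Test: log-rank, one-sided 0.025, borrowed from the CEHPI comparison; assumed for this endpoint.
- Follow-up: section 6.6 gives at least 1 year after the last randomisation. Censoring was set at 52 weeks plus a uniform 0-104 weeks.

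**Hand approximation for (b)**

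P(signal) = Φ(|ln HR| × √(d·p·(1−p)) − 1.96). Take 15 hypertensives, all 17 placebo patients and, as an upper bound, a death in every patient: d = 32, p = 15/32 = 0.469, √(32 × 0.469 × 0.531) = 2.82.
- HR 0.7: 0.357 × 2.82 − 1.96 = −0.95, giving 0.17.
- HR 0.67: 0.400 × 2.82 − 1.96 = −0.83, giving 0.20 (simulated: 0.19).

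**Simulation** (exponential OS, hypertension independent of survival; 6,000 trials per setting for most entries)

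| Drug HR | (a) | (b) | (c) | any of (a)-(c) |
|---|---|---|---|---|
| 1.0 | 0.025-0.029 | 0.030 | 0.022 | 0.055-0.056 |
| 0.7 | 0.025-0.028 | 0.15-0.16 | 0.06 | 0.17 |
| 0.6 | 0.024-0.026 | 0.24-0.26 | 0.08 | 0.25-0.27 |

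Reading (d) gave about 0.05 at HR 0.7. With no drug effect it was 0.023 (10% placebo hypertension).

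The apparent hypertension HR at a drug HR of 0.67 was 1.02 for (a), 0.66 for (b), 0.86 for (c) and 0.90 for (d). Reading (b) thus returns the drug effect itself, and (c) and (d) return part of it.

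**Sensitivity at drug HR 0.67**
- Hypertension on Axitinib from 25% to 60%: 0.12-0.21 for (b), 0.04-0.10 for (c).
- Control medians of 4 and 6 months: 0.17-0.18 for (b).

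**Choice among contrasts with no drug effect**

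0.055 / 0.025 = 2.2 times the assumed level.

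**What naming the arm does not cure**

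The near-nominal rates for (a) arise because the simulation draws hypertension independently of survival. When onset can occur only while the patient is alive, with no drug effect and assumed onset patterns, (a) gave false signals in about 8-15% of trials for early or treatment-limited onset. It reached about 90% in an extreme case with constant onset throughout survival.

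**The case against.** The strongest case against has five parts.

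- **Size depends on the reading.** The large figures belong to the placebo-only comparator. The word combined fits (c) or (d) at least as well, and there the distortion is modest (0.05-0.06 at HR 0.7). This stands.
- **A drug effect is assumed.** With none, each single contrast is near nominal. If there is one, the OS comparison between arms is itself a listed secondary endpoint, so a reader would see both results. This stands as mitigation; it does not make the contrast interpretable.
- **No test level is assigned.** The sentence in 9.2 may mean only a ROC analysis. A reader might infer that the plan breaches its own 0.025 level. The documents do not support that, because they never attach this level to diastolic pressure.
- **The within-arm contrast is not valid by itself.** It is the reading most exposed to immortal time in the no-drug-effect runs, and one arm cannot separate a prognostic from a predictive marker. Both points stand and shape the fix.
- **An arm-by-pressure interaction is hardly estimable.** 17 × 0.10 = 1.7 and 17 × 0.20 = 3.4, so about 2-3 placebo hypertensives. None would be seen with probability 0.90^17 = 0.17 at a 10% rate, or 0.85^17 = 0.06 at 15%. This stands.

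None of this supplies the missing comparator.

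**Conclusion.** The comparator is undefined in all three places, and the wording lets placebo patients in without adjustment for arm. If Axitinib affects OS, those readings carry part or all of the drug effect. At an assumed drug HR of 0.7 and an assumed one-sided 0.025, false hypertension signals are about 0.16 against placebo, 0.06 against both arms combined and 0.05 pooled over arms, compared with 0.03 within Axitinib. With no drug effect the cost is the freedom to choose, about 0.055 over three contrasts. These figures rest on 33:17 allocation, a 5-month control median, 44% hypertension on Axitinib and uninformative hypertension.

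A reader might infer that the plan commits to a placebo comparator and must produce a false marker. It permits that reading but does not require it. A reader might also infer that the main conclusions are at risk. They are not: this is one of eight secondary endpoints in a pilot that disclaims adequate powering, and the triggers for further study in section 9.1 rest on PFS and on survival by CEHPI response. The wording should still be corrected, at little cost.

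**What to change.** 1. In the Trial Summary, section 2.1 and section 2.2, replace the qualification about placebo and treatment groups with one contrast: within the Axitinib arm, OS in patients with v without new diastolic pressure above 90 mmHg.
2. In section 9.2, state that this survival analysis uses that contrast and is exploratory.
3. In the same place, define pressure status either at a landmark (for example the 8-week visit, among patients alive then, with OS counted from that visit) or as a time-dependent covariate.
4. If placebo patients are used, adjust for or stratify by arm, and report placebo outcomes by pressure status descriptively. An interaction estimate would be very imprecise.

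**Cost.** A few sentences and no new data. The comparison uses about 33 patients instead of up to 50, so its interval is wider. A landmark loses more: with exponential survival at medians of 4, 5 and 6 months, the proportion alive at 8 weeks is 0.5^(8/17.4) = 0.73, 0.5^(8/21.7) = 0.77 and 0.5^(8/26.1) = 0.81. That leaves about 24 to 27 of 33 if Axitinib has no effect. The time-dependent covariate keeps all 33. Neither form can show whether the marker is predictive or only prognostic, and the report should say so.
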